1.1 Full title of study

The detection and prognosis of perinatal depression: a prospective validation of the National Institute for Health and Clinical Excellence (NICE)-endorsed ultra-brief questions.

1.2 Acronym

BABY PaNDA Study: Born And Bred in Yorkshire: PeriNatal Depression Diagnostic Accuracy Study

1.3 HS&DR Reference

11-2004-23

2 Background

Depression accounts for the greatest burden of disease among all mental health problems, and is expected to become the second-highest amongst all general health problems by 2020 (1). Depression during pregnancy and/or early motherhood (perinatal depression) is an important category of depression in its own right.

Perinatal depression affects up to 20% of women (2) and can lead to a variety of adverse outcomes. Depression during pregnancy (prenatal depression) has been shown to be associated with adverse neonatal outcomes, poor self-reported health, substance abuse and alcohol abuse, and poor usage of antenatal care services (3). There is now considerable evidence to show that postnatal depression (depression following the birth of a child) has a substantial impact on the mother and her partner (4), the family (5), mother-baby interactions (6) and on the longer-term emotional and cognitive development of the baby (7), especially when depression occurs in the first year of life (8). Unfortunately, despite such adverse consequences, less than

50% of cases of perinatal depression are detected by healthcare professionals in routine clinical practice (2).

The use of case-finding and screening strategies to detect perinatal depression has been advocated. The National Service Framework (NSF) made an explicit requirement that all areas should have local protocols for the management of postnatal depression (9). In practice, screening and case-finding strategies have tended to focus upon the routine or ad-hoc administration of the Edinburgh Postnatal Depression Scale (EPDS) in the postnatal period. Such NSF screening strategies have attracted substantial controversy (10). Criticisms of such a strategy are based upon the ethics of mass screening, the psychometric properties of available screening instruments (such as the EPDS), the acceptability (both to patients and healthcare professionals) of screening and case-finding strategies, and the absence of any evidence that screening, per se, leads to effective management and improved mother and infant outcomes (11).

It was in this context that the National Institute for Health and Clinical Excellence (NICE) produced recommendations on the psychological care of women around the time of childbirth (12). NICE recommended the use of ultra-brief screening (2-3 item) questions to aid the identification of depression (12) (see Box 1). These questions are often referred to as the Whooley questions (13). However, this recommendation was made despite the absence of definitive validation studies of the ultra-brief depression screening questions in a perinatal population. NICE also recommended that the ultra-brief screening questions be validated against a diagnostic gold standard, and against the EPDS (12).

NICE guidance therefore has been offered in the absence of research evidence and national screening policy (as issued by the National Screening Committee, NSC) (14) is not informed by sound research. The BABY PaNDA study will close this evidential gap in time for the next revisions of NICE guidance and NSC policy. We have conducted a systematic review, commissioned by the NIHR HTA programme, of existing perinatal mental health research (15). We have since updated this review and there remain no published validation studies of the NICE ultra-brief depression screening questions (16). BABY PaNDA builds upon pilot work where we have tested the feasibility of longitudinal validation across the perinatal period in NHS services, and produced a preliminary estimate of diagnostic properties of the NICE ultra-brief questions (17). BABY PaNDA addresses the need to replicate these results in a larger sample of women with a different and wider geographical population.

- 1 "During the past month, have you often been bothered by feeling down, depressed or hopeless?"
- 2. "During the past month, have you often been bothered by having little interest or pleasure in doing things?"A third question should be considered if the woman answers "yes" to

either of the initial screening questions:

3. "Is this something you feel you need or want help with?"

Box 1: Ultra-brief screening questions for identifying depression recommended by NICE (12).

The need for good prospective epidemiological estimates of perinatal depression and psychological co-morbidity has been identified in the most recent policy recommendation issued by the UK NSC (14). The natural history of depression during the perinatal period is under-researched with postnatal depression having received considerably more attention than prenatal depression. The finding that less than 50% of cases of perinatal depression are recognised is largely drawn from cross-sectional studies of postnatal depression. Consequently, we do not know the degree to which prenatal depression sufferers continue to be symptomatic in the postnatal period and what numbers of women with postnatal depression are 'new cases'. The BABY PaNDA study will allow us to examine the relationship between depression before and after birth.

Epidemiological research shows that depression commonly co-exists with other common mental health disorders such as general anxiety and somatoform complaints. This is important since assessments of depression without the recognition of co-existing psychological symptoms will lead to suboptimal treatment strategies. There is an increasing need for psychosocial interventions that address the range of co-morbid symptoms that are present and the rational use of such interventions should be informed by epidemiological estimates of need. Recent NICE guidance (18) has highlighted the importance of psychological co-morbidity. However, the issue of co-morbidity is not well understood in perinatal mental health research. The BABY PaNDA study seeks to address this knowledge gap by using a structured gold standard diagnostic interview to capture the full range of common mental health disorders.

Our previous research has shown that there are limited studies into the acceptability of routine screening and case-finding for postnatal depression (15, 19). If depression screening questions are to be used in routine clinical practice, then they should be acceptable to both expectant and new mothers and to healthcare professionals. Our research will therefore inform the implementation of the NICE-endorsed screening strategy based on expectant and new mothers' and healthcare professionals' acceptability of the depression screening tools and assessment of potential implications for the care pathway for women diagnosed with perinatal depression.

There is concern that screening for perinatal depression is not an efficient way of improving the quality of healthcare for new mothers. The additional health benefit which accrues from screening programmes may be limited by a number of factors, including the uptake and the degree to which additional cases are well managed and respond to treatment. The enduring criticism of psychological screening programmes is that they identify less severe disorders, and that such disorders would have remitted anyway without the provision of intervention. We have previously addressed this issue in a state of the art decision model (15, 20) to help understand the important clinical and economic drivers of cost-effectiveness in relation to routine screening and case-finding for postnatal depression. Our model was limited by the availability of primary research on diagnostic utility; on estimates of the

temporal stability of screening scores and the natural history of screenpositive depression across the perinatal period. The BABY PaNDA study will help populate this existing decision model and will enable us to produce the best estimates of cost effectiveness in relation to routine screening and case finding for perinatal depression.

This prospective validation study will fill an important evidential gap and have an immediate impact on NHS patients and services by informing NICE guidance and UK NSC policy, which will enable the NHS to plan services and make informed decisions on the basis of screening results.

3 Research Objectives

This is an integrated health services research project which combines epidemiological, psychometric, qualitative and health economic methods to meet a series of objectives which emerge from a clinically-important topic.

The BABY PaNDA study will be a prospective validation of two depression screening tools (the ultra-brief NICE depression screening questions and the EPDS) against a diagnostic gold standard in a perinatal population. The study will include a concurrent economic and qualitative evaluation. The BABY PaNDA study research objectives are:

- Instrument Validation: To validate the ultra-brief NICE-endorsed depression screening questions and the Edinburgh Postnatal Depression Scale (EPDS) against a diagnostic gold standard at 20 weeks pregnancy and at 3-4 months post-birth.
- 2. Longitudinal Assessment: To judge the temporal stability of positive and negative screens between pre- and post-birth, and to ascertain whether there is an optimum time to screen for perinatal depression.

- 3. Standardised Diagnostic Assessment of Co-Morbidity: To examine the co-existence of depressive symptoms alongside common mental health problems.
- 4. Evaluation of Acceptability: To determine the acceptability (to expectant and new mothers and healthcare professions) of the NICE ultra-brief depression screening questions and the EPDS during the perinatal period, and the potential implications for the care pathway.
- Estimation of Cost-Effectiveness: To assess the cost-effectiveness of the NICE ultra-brief depression screening questions against the EPDS for routine screening for perinatal depression in maternity services.

4 Methods

4.1 Design

The BABY PaNDA study will be a prospective validation study. The study will be embedded within the framework of the existing BABY (Born and Bred in Yorkshire, www.bornbredyorks.org) cohort study (see appendices 1 & 2 for flow diagrams of the BABY and BABY PaNDA studies).

4.1.1 The BABY cohort

BABY is a population-based cohort of babies and their parents and is a collaborative project between the Hull York Medical School (HYMS, www.hyms.ac.uk); the Mental Health & Addictions Research Group (MHARG, www.mharg.york.ac.uk) and the Epidemiology & Cancer Statistics Group (ECSG, www.ecsg.york.ac.uk) within the Department of Health Sciences at the University of York; and colleagues within local NHS Trusts.

Established in 2011, BABY provides a comprehensive cohort of women recruited during pregnancy, their partners and babies. In the BABY cohort we collect data on maternal and infant health during the antenatal period, labour and the neonatal period, gathered primarily via routine systems from medical records. Data are also collected on the psychological wellbeing of mothers and their partners during pregnancy and for one year after their baby's birth, gathered directly from parents via questionnaires. The BABY cohort has a target population of more than 10,000 births a year. Women (and their partners) are invited to take part in the BABY cohort at approximately 12-14 weeks of pregnancy (see BABY study protocol for detailed information).

A motivating design principle of the BABY cohort is therefore to measure the psychological wellbeing of all mothers taking part. Such information will allow us to establish population norms for the commonly used routine measures of psychological wellbeing, against which we can compare the outcomes of women taking part in BABY PaNDA. This is important since there are very little data in this area. In addition, all mothers participating in the BABY cohort will contribute to the BABY PaNDA study. Data collected from all BABY mothers, including self-report measures of psychological wellbeing at three time points – once during pregnancy and twice after birth – as well as obstetric and neonatal data collected from maternity records, will be used to interpret the BABY PaNDA outcomes. This will allow us to contextualise findings from BABY PaNDA against the larger BABY population cohort.

4.1.2 Instrument Validation, Longitudinal Assessment & Standardised Diagnostic Assessment of Co-Morbidity

The two depression screening tools - the NICE ultra-brief depression screening questions and the EPDS - will be validated against a WHO (World Health Organisation) diagnostic gold standard clinical assessment of depression (International Classification of Disease, ICD-10) at two stages - 20 weeks pregnancy and 3-4 months post-birth. By cross-validating the diagnostic gold standard against scores on the two depression screening tools at these two time points in the perinatal care pathway we will be able to assess the diagnostic accuracy of these tools in terms of false positives, false negatives and true negative results. This in turn will yield measures of sensitivity, specificity and positive and negative likelihood ratios (with 95% confidence intervals) and hence the diagnostic utility of the depression screening tools. This validation method will also permit us to judge the temporal stability of positive and negative screens between pre- and post-birth and the natural history of screen-positive depression across the perinatal period. This will also enable us to ascertain the persistence of early screens in predicting longer-term problems. This will provide important information on the nature of the relationship between depression before and after birth.

A diagnostic assessment of co-morbidity will be made in two ways: by using previously validated questionnaires and by using the WHO diagnostic gold standard structured interview to ascertain the presence of common mental health problems, such as anxiety disorders and somatoform complaints (physical symptoms with a lower probability of physical pathology). An assessment of psychological co-morbidity will be made at three time points during pregnancy and early motherhood: 20 weeks pregnancy, 3-4 months post-birth and 1 year post-birth. This will allow us to examine the co-existence of depressive symptoms alongside other common mental health problems during the perinatal period. This will inform the delivery of psychosocial treatments by mental health practitioners to take account of other common mental health problems, such as anxiety and somatic complaints.

4.1.3 Evaluation of Acceptability

The aim of the qualitative evaluation is to investigate the acceptability and impact of the NICE ultra-brief depression screening questions and the EPDS and the extent to which they each capture appropriate information for effective screening of depression in perinatal care.

Objectives of the qualitative evaluation are:

- 1. To assess the acceptability of the NICE ultra-brief and EPDS depression screening questions for women and healthcare professionals.
- To understand women's processes of answering the NICE ultra-brief and EPDS depression screening questions in terms of their understanding, confidence and recall methods.

- To explore women's perceived effectiveness of the NICE ultra-brief and EPDS depression screening questions in relation to their current and historical symptoms.
- To explore assessment of the impact of the NICE ultra-brief and EPDS depression screening questions in relation to their subsequent symptoms and experience on the care pathway.

Acceptability of the NICE ultra-brief depression screening questions and the EPDS will be evaluated among women and healthcare professionals using a mixed methods approach. This includes data collection using both a quantitative survey tool and in-depth interviews. Reported service-use data will be triangulated against medical records. Both the general acceptability of the depression screening tools and the individual questions will be interrogated.

All women who consent to take part in BABY PaNDA will complete the quantitative survey tool as part of the data collection procedure for the study (see sections 4.3 and 4.4). Additional consent for women to participate in the in-depth interviews will be sought at the point of consent to the study; women can choose not to provide consent to be approached to take part in the in-depth interviews whilst still participating in BABY PaNDA.

Quantitative survey

All women participating in BABY PaNDA will complete a brief self-report acceptability survey at two stages: 20 weeks of pregnancy and 3-4 months post-birth. The acceptability survey will be administered immediately following completion of the NICE ultra-brief depression screening questions and the EPDS. This brief survey was designed as a self-report tool to assess the acceptability of the EPDS (21) and was adapted by Mann and colleagues (17) to include an assessment of the acceptability of the NICE ultra-brief depression screening questions. For the purposes of this study, the Mann acceptability survey (17) has been further adapted to assess a range of concepts regarding the acceptability of the depression screening tools and the processes for completing the questions. This quantitative data will provide an overview of acceptability and process related issues for each of the two depression screening tools from a large and diverse sample of women. These issues will be explored in more detail in a sub-sample of women participating in semi-structured in-depth interviews.

In-depth semi-structured interviews

A purposive sub-sample of 25-30 women will also participate in a maximum of three in-depth, face-to-face interviews; if women are unable to conduct the interview face-to-face, the option of a telephone interview will be provided. Subject to data saturation, women will participate in two or three in-depth interviews following completion of the BABY PaNDA outcome measures at 20 weeks pregnancy, 3-4 months post-birth and/or 1 year post-birth (see section 4.4) to discuss their views and experience of completing the NICE ultra-brief depression screening questions and the EPDS and/or their associated experience on the care pathway. This sample is expected to achieve data saturation (22) on the complex issues underpinning acceptability of the two depression screening tools for women from different socio-economic backgrounds, age, parity, positive/negative screens for depression (based on the NICE ultra-brief depression screening questions screening questions) and study sites.

A semi-structured topic guide based on the cognitive interviewing method attributable to Tourangeau (23) will elicit recognised concepts of questionnaire acceptability, understanding, confidence in ability to answer the questions, and recall methods for each of the depression screening tools and their individual questions. Additional open-ended probes will examine the casehistory of, and experience on the care pathway for, individual women. Indepth, longitudinal interviews will be conducted by the same experienced qualitative researcher to improve the quality and depth of data collected (15).

In-depth single interviews will also be conducted among a purposive sample of 6 midwives and 6 health visitors, including diversity in age, location, professional grade and experience, to explore their experience of delivering the depression screening tools in routine clinical practice and their training needs. Interviews will be conducted face-to-face or over the telephone depending on participant preference. This will be explored against descriptions of recommended and routine practice from health professionals in the respective site

Subject to consent, interviews among women and health professionals will be audio-recorded.

4.1.4 Estimation of Cost-Effectiveness

Design and theoretical/conceptual framework

The cost effectiveness analysis will be based on a decision analytic model comparing the NICE ultra-brief depression screening questions with the EPDS for screening perinatal depression. The analysis will make a clear link between the diagnostic accuracy of the screening strategy in the study, the impact on subsequent treatment decisions and the ultimate effect on health outcomes and costs. Hence, the costs and outcomes of each of the four diagnosis groups – true positive, false negative, true negative and false positive – will to be assessed. A previously published decision model for postnatal depression (20) will be adapted for this study.

Data collection

The main outcome will be cost per quality-adjusted life year (QALY). This is because it is necessary to assess the value of improved outcomes from more accurate identification strategies in units that can be compared with those of programmes and interventions in other specialties and disease areas that are competing for finite health-care resources (24). The performance indicators for the two perinatal depression screening questionnaires and data on healthrelated quality of life and resource utilisation will be obtained from the validation study, while other parameters in the model will be derived from literature sources and relevant databases. Cost data will include the cost of administering the screening methods, the cost of any subsequent treatment, and the cost associated with incorrect diagnosis. The administration cost will be based on the time involved in administering screening. The NHS resource use during the perinatal period will be evaluated based on primary data collected from women participants using a bespoke resource utilisation questionnaire (see section 4.4). The questionnaire will be completed by women at three time points during pregnancy and early motherhood: 20 weeks pregnancy, 3-4 months post-birth and 1 year post-birth. Data will be collected on the use of community-based primary care services, hospitalbased services and the use of antidepressant medication. Unit costs of health service utilisation will be based on national reference costs (25, 26). We will also review NICE clinical guidelines on management of perinatal mental health conditions to evaluate the expected resource use during the perinatal period; subsequently, the cost parameters will be populated in the decision model. Utility values will be based on primary data collected from the women participants using health-related quality of life questionnaires at 20 weeks pregnancy, 3-4 months post-birth and 1 year post-birth. QALYs will be estimated based on utility values associated with perinatal depression.

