8.1 Monitoring and reporting adverse events

This study does not meet the requirements stipulated for a CTIMP (Clinical Trial of Investigational Medicinal Product) or a non-CTIMP as no form of intervention or treatment will be given to participants. This study is therefore not subject to any additional restrictions. We will have no influence on the participants' maternity care or the usual care they receive from their GP. Decisions about participants' treatment or prescription of medications will be made by the participant in conjunction with their GP and/or midwife. If a participant asks a member of the research team for an opinion on medical issues, they will be strongly encouraged to seek advice from their GP.

This study will record details of any Serious Adverse Events (SAEs) that are required to be reported to the Research Ethics Committee (REC) under the terms of the Standard Operating Procedures for RECs. An SAE is defined as an untoward occurrence that:

- (a) Results in death;
- (b) Is life-threatening;
- (c) Requires hospitalisation or prolongation of existing hospitalisation;
- (d) Results in persistent or significant disability or incapacity;
- (e) Consists of a congenital anomaly or birth defect; or
- (f) Is otherwise considered medically significant by the investigator.

If a participant experiences an SAE we will report this to our main REC where in the opinion of the Chief Investigator or clinical members of the Study Management Group the event was:

- 'related': that is, resulting from the administration of any of the research procedures; and
- 'unexpected': that is, a type of event not listed in the protocol as an expected occurrence.

In the context of the current study, an occurrence of the type listed in (a) to (f)

above will be reported as an SAE if:

- It is suspected to be related to an aspect of the research procedures (e.g. completion of questionnaires, participation in qualitative interviews), or
- It is an unexpected occurrence

Hospitalisations are expected in the study population as women will give birth during the course of the study and most births in the UK take place in hospital; in addition, women may require overnight hospital monitoring during their pregnancy. Hospitalisations resulting from giving birth or from monitoring during pregnancy will therefore not be reported as an SAE. SAEs that result from physical health problems will not be subject to expedited reporting.

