Appendix 2 – Flow Diagram: BABY Cohort & BABY PaNDA Studies

Appendix 3: BABY PaNDA Identification of Risk of Depression/Anxiety Protocol

Identification of Risk of Depression/Anxiety Protocol

This protocol provides the guiding principles for instances when the clinical diagnostic interview (as assessed by the Clinical Interview Schedule - Revised; CIS-R) identifies a participant as currently experiencing depression and/or anxiety.

Participants will complete the CIS-R during face-to-face assessments and during telephone assessments. All BABY PaNDA researchers will have received training on how to interpret the CIS-R output. The Identification of Risk of Depression/Anxiety protocol will be implemented following a participant assessment.

The following documents provide an overview of the processes to be followed and associated documentation:

- Identification of Risk of Depression/Anxiety Flowchart identified via face-to-face or telephone assessments
- Identification of Risk of Depression/Anxiety Form
- Clinical Contact Details

There may be instances where a different course of action needs to be implemented from those detailed here, where this is deemed clinically appropriate following consultation with a clinician. Any such instances will be documented appropriately on the Identification of Risk of Depression/Anxiety Form.

Identification of Risk of Depression/Anxiety Flowchart: Identified via face-to-face or telephone assessment

Identification of Risk of Depression/Anxiety Form

The patient below has received a 'probable primary diagnosis' of depression and/or anxiety on the CIS-R during a BABY PaNDA assessment.

Participant ID Code:			
Date of Assessment:			
Assessment: 20 weeks pregnancy / 3-4 months post-birth / 1 year post-birth			
Probably Primary Diagnosis on CIS-R:			
Depressive Episode			
Anxiety Episode			
Has participant been advised to contact their GP?: Yes No			
Has the GP/Practice Midwife been sent the Notification of Identification of			
Risk of Depression letter?: Yes No N/A			
Comments:			

Researcher Name:	 Study Site:
Research Signature:	 Date:

Name of Clinical Contact:	
Clinical Contact Signature:	Date:

.

...

Clinical Contact Details for all study sites

	Contact 1: [name]	Contact 2: [name]
Role	Clinical Lead	Chief Investigator
Landline		
Mobile		
Email	[contact]	[contact]

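### Study notification follows the CIS-R rather than the screen, so follow-up data cannot stand for missed cases, acted-on false alarms or unaltered natural history

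*Protocol*

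**What the plan says.** **Economic model.** Section 4.1.4 sets the task: "Hence, the costs and outcomes of each of the four diagnosis groups" are to be assessed by adapting a published decision model. On sources, it says that quality of life and "resource utilisation will be obtained from the validation study, while other parameters in the model will be derived from literature sources". Resource-use and utility questionnaires are completed at 20 weeks, 3-4 months and 1 year. NICE guidelines are also reviewed for expected resource use. Section 5.2.3 evaluates the effect of true and false identification on costs and QALYs over the study period.

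**Natural history.** Section 4.1.2 says the validation will permit a judgement of "the natural history of screen-positive depression across the perinatal period". The Background (section 2) names missing natural-history data as a limit of the earlier model and says this study will help populate that model.

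**What the study does on a diagnosis.** All women have the CIS-R at all three stages (section 4.4). Appendix 3 covers instances when the CIS-R "identifies a participant as currently experiencing depression and/or anxiety", and "The Identification of Risk of Depression/Anxiety protocol will be implemented following a participant assessment". Its form asks "Has participant been advised to contact their GP?: Yes No" and "Has the GP/Practice Midwife been sent the Notification of Identification of" risk letter, with the options Yes, No and N/A. Appendix 3 does not mention the screening result. In section 4.4 the screen prompts advice to see the GP only when a screen-positive woman answers yes to the help question.

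**Influence on care.** Section 8.1 states: "We will have no influence on the participants' maternity care or the usual care they receive from their GP".

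**The concern.** In a screening model, the value of sensitivity comes from the difference between a detected and an undetected case, and the cost of poor specificity comes from acting on a false alarm. Here the reference standard itself sets off a procedure. A woman the screen missed is, by definition, CIS-R positive, so the study's own procedure reaches her. A woman with a false alarm is CIS-R negative for depression, so in most respects she is handled like a true negative. After the first CIS-R, neither group shows what would follow from her screening result in routine care.

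The same applies to persistence. The Background reports that fewer than half of cases are recognised in routine practice, and cites the criticism that disorders found by screening would have remitted without intervention. Persistence measured after GP advice or notification does not answer that criticism.

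**Working it through.** **1. The plan's own sample size.** Inputs (section 5.1): expected sensitivity 0.95, lower 95% limit above 0.80 with probability 0.95, prevalence 0.20, attrition 0.34. With an exact one-sided 95% lower limit, 50 cases meet the target (probability 0.962; 49 cases give 0.903). Then 50 / 0.20 = 250, and 250 / (1 - 0.34) = 378.8, rounded up to 379. The stated figure reproduces and is not in dispute.

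**2. Who comes under which action.** Reading section 4.4 against Appendix 3:

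| Group (for depression) | Appendix 3 applies? | Action arising from the screen |
|---|---|---|
| True positive | Yes | GP advice if yes to the help question |
| False negative | Yes | None |
| False positive | Only with a CIS-R anxiety diagnosis | GP advice if yes to the help question |
| True negative | Only with a CIS-R anxiety diagnosis | None |

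The Appendix 3 column follows the diagnosis, not the test. A screening programme would follow the test.

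**3. Which data are affected.** The procedure follows an assessment. Stage 1 utilities and resource use therefore largely precede any notification; stage 2 and 3 data from women positive at an earlier stage come after it. Women first found depressed at stage 2 have had no earlier depression notification.

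**4. Expected numbers.** Cases = N x 0.20. False negatives = cases x (1 - sensitivity). False positives = non-cases x (1 - specificity). Accuracy inputs are from sections 4.4 and 5.1: ultra-brief sensitivity 95%, specificity 68% antenatal and 65% postnatal; EPDS 91% and 91%. I assume that all 34% attrition has occurred by 3-4 months. Section 4.4 gives the EPDS figures for the postnatal period, so using them at 20 weeks is also an assumption.

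| | 20 weeks, N = 379 | 3-4 months, N = 250 |
|---|---|---|
| Cases | 75.8 | 50 |
| Non-cases | 303.2 | 200 |
| False negatives, ultra-brief | 75.8 x 0.05 = 3.8 | 50 x 0.05 = 2.5 |
| False negatives, EPDS | 75.8 x 0.09 = 6.8 | 50 x 0.09 = 4.5 |
| False positives, ultra-brief | 303.2 x 0.32 = 97 | 200 x 0.35 = 70 |
| False positives, EPDS | 303.2 x 0.09 = 27 | 200 x 0.09 = 18 |

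The chance of no ultra-brief false negative at all at 3-4 months is 0.95^50 = 0.077, about 8%. If prevalence were 10% (assumption), ultra-brief false negatives would be 37.9 x 0.05 = 1.9 and 25 x 0.05 = 1.25. At the pilot's 100% sensitivity (section 4.4) there would be none.

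These counts show how thin the data on missed cases would be. They do not measure the effect of notification, which the protocol gives no means to estimate.

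**The case against.** **The plan does not say that observed averages in false-negative or false-positive women will fill those branches.** Section 5.2.3 describes a hypothetical population with a separate treatment model. Section 4.1.4 also draws on literature, databases and NICE guidelines, and ties QALYs to utilities for perinatal depression, which may mean health state rather than test result. This stands in part: the model does not rest on these women alone, and the intended source may already be external. But section 4.1.4 assigns quality of life and resource use to the study without excepting the misclassified groups, and no section addresses the effect of notification.

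**Notification may be incomplete.** The Appendix 3 flowchart is not available, and the form allows No for GP advice and No or N/A for the letter. This stands: the CIS-R trigger is explicit, but how many women are actually notified is unknown.

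**Section 8.1 can be read narrowly.** The sentence supports the study's regulatory status, and the text goes on to leave treatment decisions to the woman with her GP or midwife. That softens the conflict with Appendix 3 but does not remove it.

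**Stronger readings that the documents do not support.**
- A reader might infer that the cost per QALY is biased towards no difference between the tools. Neither direction nor size can be derived.
- A reader might infer that only stage 1 utilities are usable. Utilities by current CIS-R state at stages 2 and 3 still describe that health state, and pregnancy values cannot replace postnatal ones.
- A reader might infer that 3-4 month accuracy is compromised because some cases were already known. Screen and CIS-R are done in the same interview or within two weeks (section 4.4), so earlier notification does not of itself bias sensitivity or specificity. Excluding those women would change the target population and remove cases from about 50.

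**Conclusion.** The point holds and should be dealt with before the model is fixed. Data collected after the first CIS-R cannot represent the course or cost of an undetected case or of an acted-on false alarm, and persistence from 20 weeks is not unaltered natural history. The conclusion rests on two things the protocol states: Appendix 3 is triggered by the CIS-R without reference to the screen, and resource use and quality of life are to come from these women over the study period. It does not require every woman to have been notified.

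The extent of notification and the size and direction of any bias remain unknown. At planning values, the study's own evidence on cases missed by the ultra-brief questions would come from about 4 women at 20 weeks and 2 to 3 at 3-4 months, all within the scope of Appendix 3. The accuracy results and the utilities by current health state are not called into question.

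**What to change.** 1. **Sections 4.1.4 and 5.2.3.** State that post-screen costs, detection or treatment probabilities, and the course of missed cases and acted-on false positives come from literature or explicit assumptions varied in the probabilistic sensitivity analysis, not from stage 2-3 data observed by diagnosis group. Keep study data for test accuracy, administration time, and utilities by current CIS-R health state at all stages.
2. **Section 4.1.2 and the model inputs.** Use the notification status recorded on the Appendix 3 form to report persistence from 20 weeks as persistence under study notification. Do not enter it in the model as unaltered natural history.
3. **Section 8.1.** Reconcile the no-influence sentence with Appendix 3. No change to the notification procedure is proposed.

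The cost is some specification wording and the use of a form already completed. The downside is heavier reliance on external parameters for the two misclassified groups.
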